3.3 Tertiary

The tertiary objectives of this study are to evaluate the prognostic value of baseline ctDNA as an independent prognostic value in addition to ypstage and histology.

(Note: The plan to address the last of the secondary objectives, i.e., the cost-effectiveness analysis, and the tertiary objectives will be developed separately later.)

4. Endpoints

4.1 Primary Efficacy

The primary efficacy endpoint is the protocol specified organ preservation rate.

4.2 Secondary Efficacy

The secondary efficacy endpoints are:

- 3 year locoregional relapse rate
- 3 year distant relapse rate
- 3 year disease free survival
- Quality of life

4.3 Safety

The safety endpoints are post-operative complication rate, serious and non-serious adverse events (clinical and laboratory), laboratory parameters, dosing data (including dose interruptions, total delivered dose and dose modifications) and reasons off treatment.

5. Sample Size and Power

The expected organ preservation rate is 50-68% among patients with clinical T1-3N0 rectal tumours treated with chemoradiation and minimally invasive surgery. Based on these historic phase II data, the experimental treatment would be considered of no interest if the protocol specified organ preservation rate is 50% or lower (H_0) and as promising if its avoidance rate is 65% or higher (H_1).

An optimal two-stage minimax design would be used to test the above hypotheses, which would accrual 22 evaluable patients in the first stage. The trial would be stopped at the end of the first stage if the number of patients who avoided radical surgery is 10 or less. Otherwise the trial would proceed to the second stage to accrue 28 additional evaluable patients. The experimental procedure would be considered as promising if, out of the total patients accrued, 30 or more patients avoided radical surgery. The exact type I error rate and power of this design are respectively 0.1 and 0.8. Allowing for a 15% inevaluable rate, the total sample size would be 58 patients.

6. Data Set Descriptions

Five types of analysis samples will be used:

1. All Accrued Patients:

All patients accrued in the study.

2. All Chemotherapy Treated Patients:

All patients who have received at least one dose of FOLFOX or CAPOX.

3. All Chemotherapy & Excision Treated Patients

All patients who have received at least one dose of FOLFOX or CAPOX and TEMS or TAMIS.

4. All Chemotherapy & Excision/Surgery Treated Patients

All patients who have received at least one dose of FOLFOX or CAPOX and excision (TEMS or TAMIS) or surgery (TME).

5. All Quality of Life Evaluable Patients

All patients who have completed at least one quality of life questionnaire.

7. Statistical Analysis

7.1 General Methods

Continuous and ordinal categorical variables are summarized using the mean, median, standard error, minimum and maximum values. All confidence intervals are computed based on normal approximations except those for rates, which will be computed based on the exact method.

Percentages given in the summary tables will be rounded and may therefore not always add up to exactly 100%. Listings, tabulations, and statistical analyses will be carried out using the SAS (Statistical Analysis System, SAS Institute, North Carolina, USA) software.

Baseline evaluations will be those collected on CRF Eligibility Worksheet and Baseline Report and closest to, but no later than, the first day of study medication for treated subjects and closest to, but no later than, the date of enrollment, for subjects who were enrolled but who never received any treatment.

Laboratory results, adverse events, and other symptoms are coded and graded using the NCI CTCAE when available.

When converting a number of days to other units, the following conversion factors will be used:

1 year = 365.25 days

1 month = 30.4375 days

When either day or month of a date is missing, the missing day and/or month will be imputed by the midpoint within the smallest known interval. For example, if the day of the month is missing for any date used in a calculation, the 15th of the month will be used to replace the missing day. If the month and day of the year are missing for any date used in a calculation, the first of July of the year will be used to replace the missing date.

7.2 Study Conduct

All accrued patients are included in the analysis of study conduct.

7.2.1 Patient Disposition and Follow-up

- Number of patients accrued, treated (on study, off study), never treated (**Table 1**)
- Number of alive patients (**Table 2**)
- Median (estimated by Kaplan-Meier method) and range (minimum and maximum) (**Table 2**) of the follow-up time (months) defined as time from the day of accrual to the last day the patient is known alive (LKA) as the latest of dates of enrollment, day 1 of reporting period on CRF Chemotherapy Report, date of attendance on CRF Pre-Excision Report, date of surgery or date definitive decision was made on CRF Surgery Report, and attendance/last contact on CRF Follow-up Report and CRF Short Follow-up Report or censored at the time of death and calculated as

$$[(\text{date of death or LKA} - \text{date of accrual}) + 1]/30.4375.$$

7.2.2 Accrual Patterns

- Number of patients accrued by center (**Table 3**)
- Accrual of patients by calendar time (**Figure 1**)

7.2.3 Eligibility Violations/Protocol Deviations

Eligibility violations of inclusion or exclusion criteria are centrally reviewed by CCTG; a field (y/n) for eligibility status and reason for ineligibility is entered in the database.

A major protocol violation (MPV) is defined as a deviation from the protocol, initiated by the center or the investigator, serious enough to mean that the patient's data contributes little, if any, information on the efficacy or toxicity of the regimen under study. MPVs are coded by CCTG based on its standard codes.

- Number of patients eligible, not eligible (**Table 4**)
- Reasons for ineligibility (**Table 4**)
- Major protocol violations: % for each type of violations (**Table 4**)

7.3 Study Population

All accrued patients are included in the study population analyses.

7.3.1 Patient Pretreatment Characteristics

- Gender: male, female (**Table 5**)
- Age: median, minimum, maximum values; <65, ≥65 (**Table 5**)
- Race: White, Black or African American, Native Hawaiian or other Pacific Islander, Asian, Not reported (or refused), Unknown (**Table 5**)
- Height: median, minimum, maximum values (**Table 5**)
- Weight: median, minimum, maximum values (**Table 5**)
- BSA: median, minimum, maximum values (**Table 5**)
- ECOG Performance Status: 0, 1 (**Table 5**)
- Months from first histological diagnosis of colorectal cancer to enrollment: median, minimum, maximum values (**Table 5**)
- Tumour Invasion based on pelvic MRI: submucosa, muscularis propria, muscularis propria no more than 5 mm into the subserosa/perirectal tissue, muscularis propria more than 5 mm into the subserosa/perirectal tissue, not visible on pelvic MRI (**Table 5**)
- cT-stage: T1, T2, T3a, T3b (**Table 5**)
- Tumour Height from anal verge (cm): median, minimum, maximum values (**Table 5**)

7.3.2 Baseline Pathology Results

- Longest dimension of Invasive Carcinoma: median, minimum, maximum values (**Table 6**)
- Histology: adeno-carcinoma, etc. (**Table 6**)
- Histologic grade: well differentiated, moderately differentiation, not stated in report (**Table 6**)
- Deepest layer of invasion: Mucosa, Lamina Propria, Muscularis mucosa, Submucosa, Muscularis propria, Serosa, Perirectal tissue, Subserosa, Not Stated in Report (**Table 6**)
- Depth of invasion into subserosa: median, min-max (**Table 6**)
- Deep margin: positive for invasive carcinoma, negative, not stated in report, not applicable; median, minimum, maximum values (**Table 6**)
- Mucosal margin: positive for invasive carcinoma, negative, not stated in report, not applicable; median, minimum, maximum values (**Table 6**)
- Pathologic T stage: T0, T1, T2, T3, unknown (**Table 6**)
- Number of nodes examined: median, minimum, maximum values (**Table 6**)
- Number of nodes with tumour: median, minimum, maximum values (**Table 6**)

- Tumour deposits: yes, no (**Table 6**)

7.3.3 Baseline Exams

- Sigmoidoscopy/colonoscopy: normal, abnormal non-malignant, abnormal malignant (**Table 7**)
- Other radiology investigations: normal, abnormal non-malignant, abnormal malignant (**Table 7**)
- Hematology: Hemoglobin, WBC, absolute neutrophil count (ANC), neutrophils, platelets, lymphocytes, basophils, monocytes, eosinophils (**Table 8**)
- Biochemistry: serum creatinine, total bilirubin, ALT, creatinine clearance (**Table 9**)
- Coagulation: PT, INR, PTT (**Table 10**)
- Baseline symptom status (**Table 11**)

7.3.4 Concomitant Medications and Major Medical Problems at Baseline

- Number of patients with concomitant Medication (**Table 12**)
- Number of patients with other past and current major medical problems ongoing at baseline (**Table 13**)

7.3.5 Tobacco Smoking History at Baseline

- Ever smoked any tobacco product: Yes, No, Unknown (**Table 14**)
- Currently smoking: Yes, No (**Table 14**)
- Current average number of cigarettes per day: median, minimum, maximum (**Table 14**)
- Years from quitting smoking to enrollment: median, minimum, maximum (**Table 14**)
- Years from beginning smoking cigarettes to enrollment: median, minimum, maximum (**Table 14**)
- Total number of years of smoking cigarettes: median, minimum, maximum (**Table 14**)
- Average number of cigarettes smoked per day: median, minimum, maximum (**Table 14**)
- Average pack years of cigarettes smoked: median, minimum, maximum (**Table 14**)

7.4 Extent of Neoadjuvant Chemotherapy Exposure

Patients included are those who received at least one dose of FOLFOX or CAPOX as defined in Section 6.

7.4.1 Duration of Chemotherapy

During protocol treatment, the patients are planned to receive either FOLFOX infusion on a 14 day cycle (IV oxaliplatin 85 mg/m² and leucovorin 400 mg/m² over 2 hours on day 1 and bolus fluorouracil 400 mg/m² over 5 - 15 minutes and continuous infusion of fluorouracil 2400 mg/m² over 46 to 48 hours on days 1-2) for a total of 6 cycles or CAPOX on a 21 day cycle (IV oxaliplatin 130 mg/m² over 2 hours on day 1 and 1000 mg/m² capecitabine orally twice daily for 14 days from day 1) for a total of 4 cycles.

Duration of a neoadjuvant chemotherapy treatment (in weeks) during the study is

defined as follows:

- For patients on FOLFOX:
[last date of the treatment – first date of the treatment + 14]/7,
- For patients on CAPOX:
[last date of the treatment – first date of the treatment + 21]/7

where the first and last date of the treatment are taken from respective treatment administration section of CRF Chemotherapy Report.

The following variables will be summarized using the data set of all chemotherapy treated patients:

- Number of patients by cycle of chemotherapy (**Table 15**)
- Total number of cycles of chemotherapy per patient (**Table 16**)
- Total treatment duration (weeks) per patient (**Table 17**)

7.4.2 Modifications of Neoadjuvant Chemotherapy

The administration of a neoadjuvant chemotherapy drug in a cycle may be modified (given early, delayed, omitted, reduced, interrupted, discontinued, increased, or the infusion rate was increased or decreased) because of toxicity or other reasons. For each drug, the following variables will be summarized using the data set of all chemotherapy treated patients:

- Number of patients with at least one cycle with modifications to administration (**Table 18**)
- Number of patients with modifications to administration by cycle (**Table 18**)
- Reason for these modifications (**Table 18**)

7.4.3 Cumulative dose, dose intensity and relative dose intensity

The cumulative dose (mg/m^2) per patient for capecitabine, oxaliplatin, leucovorin and fluorouracil (bolus and continuous) is defined as the sum over all cycles of the total actual dose received divided by the BSA in a given cycle.

The actual dose intensity ($\text{mg}/\text{m}^2/\text{week}$) per patient for capecitabine, oxaliplatin, leucovorin and fluorouracil (bolus and continuous) is defined as the cumulative dose (mg/m^2) divided by “treatment duration” (in weeks), where “treatment duration” per patient is defined as the duration from first day of drug administration to the last day of drug administration plus 14 days (for patients on FOLFOX) or 21 days (for patients on CAPOX) over all cycles in which the given drug is prescribed.

The median and range of cumulative dose and actual dose intensity will be summarized in respectively **Table 19** and **Table 20**.

The relative dose intensity per patient is defined as the actual dose intensity ($\text{mg}/\text{m}^2/\text{week}$) divided by the planned weekly dose as assigned in the protocol (42.5 $\text{mg}/\text{m}^2/\text{week}$ for oxaliplatin, 200 $\text{mg}/\text{m}^2/\text{week}$ for leucovorin, 200 $\text{mg}/\text{m}^2/\text{week}$ for bolus fluorouracil, and 1200 $\text{mg}/\text{m}^2/\text{week}$ for continuous fluorouracil for patients on FOLFOX; 43.3 $\text{mg}/\text{m}^2/\text{week}$ for oxaliplatin and 9333.3 $\text{mg}/\text{m}^2/\text{week}$ for capecitabine for patients on CAPOX). The patient relative dose intensities will be grouped according

to the following categories: < 60%, $\geq 60\% - < 80\%$, $\geq 80\% - < 90\%$, $\geq 90\%$ (**Table 21**).

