Neurological	Neurotoxicity grade 2 persisting between treatment cycles	Oxaliplatin	Continue FOLFOX with previous dose level of 5-FU and one dose level reduction of oxaliplatin for all subsequent cycles.
	Neurotoxicity grade 3 resolving to \leq grade 2 between treatment cycles		Continue FOLFOX with previous dose level of 5-FU and one dose level reduction of oxaliplatin for all subsequent cycles.
	Neurotoxicity grade 3 persisting between treatment cycles		Discontinue oxaliplatin. Continue 5-FU/leucovorin. Reassign to 5FUCMT if has not completed at least 5 cycles of FOLFOX.
	Neurotoxicity grade 4		Discontinue oxaliplatin. Continue 5FU/leucovorin. Reassign to 5FUCMT if has not completed at least 5 cycles of FOLFOX.
Cardiovascular	Cardiac ischemia or infarction grade 3 or 4		Discontinue all study therapy.
	Cerebrovascular ischemia grade 3 or 4		Discontinue all study therapy.

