7.1.4 Duration of Therapy

In the absence of unacceptable toxicities or disease progression, as defined in Section 10.1, or intolerable toxicity, chemotherapy will continue until completion of 6 cycles for FOLFOX and 4 cycles for CAPOX.

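### Relative dose intensity (SAP 7.4.3) drops cycles missed at the end of the course, so for day-1 drugs Table 21 can band early stoppers above patients who completed with a delay

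*SAP*

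**What the plan says.** SAP 7.4.3 builds three quantities for each drug.

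- **Cumulative dose** is "the sum over all cycles of the total actual dose received divided by the BSA in a given cycle".
- **Actual dose intensity** is that total divided by a treatment duration in weeks. The duration is "the duration from first day of drug administration to the last day of drug administration plus 14 days (for patients on FOLFOX", with 21 days in place of 14 for CAPOX, taken "over all cycles in which the given drug is prescribed".
- **Relative dose intensity (RDI)** is the actual dose intensity divided by a planned weekly dose, for example 42.5 mg/m²/week for oxaliplatin on FOLFOX. Table 21 sorts patients into four bands: below 60%, 60% to below 80%, 80% to below 90%, and 90% or more.

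The treatment is a fixed course. Protocol 7.1.4 states that "chemotherapy will continue until completion of 6 cycles for FOLFOX and 4 cycles for CAPOX", and SAP 7.4.1 repeats the same cycle numbers.

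The protocol also foresees incomplete courses. For persistent grade 3 neurotoxicity the FOLFOX table in 7.1.3.1 reads "Discontinue oxaliplatin. Continue 5-FU/leucovorin. Reassign to 5FUCMT if has not completed at least 5 cycles of FOLFOX". Sections 7.1.1.1 and 7.2 deal with patients who cannot tolerate six cycles of FOLFOX.

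**The concern.** The duration stops one cycle after the drug's last dose. A cycle omitted in the middle of the course lowers RDI, because the time still counts. A cycle omitted at the end does not, because its time disappears along with its dose. Stopping for toxicity produces exactly this second pattern.

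A reader of a banded table for a fixed 6- or 4-cycle course is likely to take 90% or more to mean that nearly all of the assigned treatment was given. Under this definition that band can hold a patient who received one cycle, while a patient who received every cycle with a delay sits below. The distortion runs in the direction that flatters tolerability.

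**Working it through.** **Inputs.** SAP 7.4.1 gives "FOLFOX infusion on a 14 day cycle" with "IV oxaliplatin 85 mg/m² and leucovorin 400 mg/m² over 2 hours on day 1", for six cycles. CAPOX has oxaliplatin 130 mg/m² on day 1 and capecitabine 1000 mg/m² twice daily for 14 days, in 21-day cycles, for four cycles. The duration rule and the planned weekly doses come from SAP 7.4.3.

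**The plan's own figures.** Planned weekly dose is dose per cycle divided by weeks per cycle:

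- FOLFOX: oxaliplatin 85/2 = 42.5; leucovorin 400/2 = 200; bolus 5-FU 400/2 = 200; continuous 5-FU 2400/2 = 1200.
- CAPOX: oxaliplatin 130/3 = 43.3; capecitabine 1000 × 2 × 14/3 = 9333.3.

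All six match SAP 7.4.3. Six on-time cycles of oxaliplatin give 510/12 = 42.5 mg/m²/week, RDI 100%, as they should.

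**Stopping early.** For *n* full-dose, on-time FOLFOX cycles, the duration is [14(*n* − 1) + 14]/7 = 2*n* weeks, so RDI = (85*n*/2*n*)/42.5 = 100% for every *n*.

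| Oxaliplatin cycles given (FOLFOX) | Dose, mg/m² | Duration, weeks | RDI | Share of 510 mg/m² |
|---|---|---|---|---|
| 1 | 85 | 2 | 100% | 16.7% |
| 2 | 170 | 4 | 100% | 33.3% |
| 3 | 255 | 6 | 100% | 50.0% |
| 4 | 340 | 8 | 100% | 66.7% |
| 5 | 425 | 10 | 100% | 83.3% |
| 6, on time | 510 | 12 | 100% | 100% |
| 6, one 14-day delay | 510 | 14 | 85.7% | 100% |

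Last row: (70 + 14 + 14)/7 = 14 weeks; 510/14 = 36.43; 36.43/42.5 = 85.7%, in the 80% to below 90% band.

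**Same dose, different score.** Missing only cycle 3 gives 425/12/42.5 = 83.3%, with the duration run from first to last administration. Missing only cycle 6 gives 425/10/42.5 = 100%. Both patients received 425 mg/m².

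**Full dosing before the stop is not needed.** Three cycles at 85 and one at 65 mg/m² (level −1 in protocol 7.1.3.1), on time, then stop: 320/8/42.5 = 94.1%, against 320/510 = 62.7% of plan.

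**CAPOX oxaliplatin.** One of four cycles: (130/3)/43.33 = 100%, for 130/520 = 25% of plan. Four cycles with a 14-day delay: 520/14/43.33 = 85.7%.

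**Capecitabine does not follow this pattern.** If its last administration is day 14, one full cycle gives 28000/[(13 + 21)/7]/9333.3 = 61.8%, and four full on-time cycles give 112000/[(76 + 21)/7]/9333.3 = 86.6%. That is a separate feature of the same definition.

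**Sensitivity to day counting.** Adding one day to the duration gives 85/(15/7)/42.5 = 93.3% for the one-cycle patient and 510/(99/7)/42.5 = 84.8% for the delayed completer. The bands do not change.

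**The case against.** The strongest reply is that dose intensity is a rate. It is meant to fall with delay, and it is not meant to measure completion, which the SAP reports elsewhere. That is fair. Intensity while on drug is a legitimate quantity, and changing its denominator would be a debatable choice of convention. What remains is that Table 21 does not say that this is the quantity shown.

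Three stronger readings are tempting, and the documents do not support them.

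- *A reader might infer that under-treatment could not be seen in the report.* It can. Table 15 counts patients at each cycle by regimen. Table 18, as specified in SAP 7.4.2, gives modifications for each drug by cycle with reasons, including omission and discontinuation. Table 22 gives reasons for coming off chemotherapy, and Table 42 the adverse events that led to it. None of these gives each patient's share of the assigned dose.
- *A reader might infer that a listed safety endpoint is misreported.* SAP 4.3 names total delivered dose, which corresponds to the cumulative dose in Table 19. RDI is not named there, and the duration rule does not touch Table 19.
- *A reader might infer that every drug scores 100% after an early stop.* The 100% result belongs to drugs given on day 1, not to capecitabine.

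It can also be argued that a drug stopped early still counts as prescribed in later cycles. On that reading, a patient who stops only oxaliplatin after cycle 1 scores 85/12/42.5 = 16.7%. This is the less natural reading, and a patient who stops all chemotherapy after cycle 1 still scores 100% under it.

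**Conclusion.** The point holds for drugs given on day 1. RDI in SAP 7.4.3 takes no account of the planned number of cycles. Oxaliplatin stopped after 1 to 5 of 6 full-dose, on-time FOLFOX cycles scores 100% each time, and six full cycles with one 14-day delay score 85.7%, so Table 21 can rank an early stopper above a completer.

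This rests on reading the duration as drug-specific and ending with that drug's last administration, and the exact 100% assumes full, on-time dosing before the stop. The documents do not say how many patients stopped early, so the effect on the counts in Table 21 is unknown. RDI is descriptive: it feeds no hypothesis test, stopping rule or efficacy estimate, and the primary endpoint is unaffected. The correction is worth making because it is cheap and because Table 21 is the only dose table set against the plan.

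**What to change.** Keep the current calculation, but label it in SAP 7.4.3 and Table 21 as relative dose intensity while on drug. Add to Table 21, for each drug and with the same four bands:

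delivered fraction = cumulative dose / planned course dose.

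Planned course doses in mg/m², from SAP 7.4.1:

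- FOLFOX: oxaliplatin 6 × 85 = 510; leucovorin 6 × 400 = 2400; bolus 5-FU 6 × 400 = 2400; continuous 5-FU 6 × 2400 = 14400.
- CAPOX: oxaliplatin 4 × 130 = 520; capecitabine 4 × 14 × 2 × 1000 = 112000.

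The delivered fraction does not depend on how the treatment duration or the word prescribed is read.

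Using the larger of actual duration and the planned 12 weeks as denominator is a different measure and should not be presented as equivalent. Both give 16.7% to the patient who stops oxaliplatin after one FOLFOX cycle, but the delayed completer stays at 85.7% under the longer duration and is 100% under the delivered fraction.

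The cost is one derived variable and a few added rows. The numerators are already computed for Table 19, and no new data are needed. The downside is that the added figure will be less favourable wherever patients stopped early. Only the analysis definition changes; no dose or treatment rule is involved.

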7.1.1 Drug Administration

7.1.1.1 **FOLFOX (5-fluorouracil + leucovorin + oxaliplatin)**

Agent(s)	Dose	Route	Duration	Schedule
Oxaliplatin	85 mg/m ²	IV over 2 hours	Day 1	Repeat every 14 days for a total of 6 cycles
Leucovorin	400 mg/m ² bolus	IV over 2 hours	Day 1	Repeat every 14 days for a total of 6 cycles
5FU	400 m/m ² bolus over 5 - 15 minutes then 2400 mg/m ² continual infusion over 46 - 48h total dose	IV	Days 1 to 2	Repeat every 14 days for a total of 6 cycles

1. Oxaliplatin could be administered first, prior to leucovorin; or concurrently with leucovorin administered via separate infusion containers.
2. If necessary to accommodate holidays, patient schedule or other justified circumstance, the schedule may be delayed up to 7 days.
3. Patients who cannot tolerate six cycles of FOLFOX or those that require dose modification below dose level -2 (see Section 7.1.3.1) may receive preoperative 5FU chemoradiotherapy based on investigator decision. If chemoradiotherapy is given, it should be given according to local institutional guidelines for FOLFOX administration. There are no restrictions on dose modifications for the 6th cycle of neoadjuvant FOLFOX.
4. Alternate folinic acids (i.e. levo-leucovorin) may be substituted for Leucovorin if not available. Note: Levo-leucovorin is twice as potent as leucovorin; dosages should be adjusted accordingly. Dosages are at the discretion of the treating physician. Dose modifications of leucovorin up to and including omission of leucovorin or its analogues imposed by drug shortages will not constitute protocol violations.
5. The dose modification schema for FOLFOX (see Section 7.1.3.1) is suggested. Oncologists may use clinical judgment in making dose modifications that deviate from the suggested schema. These will not constitute protocol violations.

7.1.1.2 ***CAPOX (capecitabine + oxaliplatin)***

Agent(s)	Dose	Route	Duration	Schedule
Capecitabine	1000 mg/m ² BID	PO	14 days starting on Day 1	Repeat every 21 days for a total of 4 cycles
Oxaliplatin	130 mg/m ²	IV over 2 hours	Day 1	Repeat every 21 days for a total of 4 cycles

1. Patients must be counseled about the importance of compliance with capecitabine. Compliance, with mention of missed doses, must be documented in the patient's medical record by site study personnel.
2. Missed doses must be documented on the appropriate CRF and by patients on their provided diary.

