7.4.4 Off Neoadjuvant Chemotherapy

The reason for off neoadjuvant chemotherapy will be taken from Off Neoadjuvant Chemotherapy Section of CRF Chemotherapy Report.

The following information will be summarized (**Table 22**):

- Number of patients off neoadjuvant chemotherapy
- Reason off neoadjuvant chemotherapy

7.5 **Surgical Treatments**

Tumour excision are performed within 2-5 weeks (for patients on FOLFOX) or 3-6 weeks (for patients on CAPOX) after first dose of last cycle of chemotherapy after a pre-excision visit performed within 2 weeks after the first dose of the last cycle (cycle 6) of FOLFOX therapy or within 3 weeks after the first dose of the last cycle (cycle 4) of CAPOX. Information from pre-excision visit and on the surgical treatment will be taken respectively from the CRF Pre-Excision Report and CRF Surgery Report.

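### The SAP 7.4.3 duration rule overshoots by 13 days for capecitabine, so four full-dose, on-time CAPOX cycles score 86.6% relative dose intensity instead of 100%

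*SAP*

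**What the plan says.** SAP 7.4.3 defines actual dose intensity, drug by drug, as cumulative dose in mg/m² divided by a treatment duration in weeks. The duration starts on the first day the drug is given and runs "to the last day of drug administration plus 14 days (for patients on FOLFOX) or 21 days (for patients on CAPOX"). A closing phrase limits this span, "over all cycles in which the given drug is prescribed", and so makes the duration specific to each drug. Relative dose intensity is this figure divided by a planned weekly dose, which for capecitabine is 9333.3 mg/m²/week. Table 21 groups the result as below 60%, 60 to below 80%, 80 to below 90%, and 90% or more.

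SAP 7.4.1 uses the same increment for the overall length of CAPOX: "last date of the treatment – first date of the treatment + 21]/7". On the source of those two dates, that section gives only this: "where the first and last date of the treatment are taken from respective treatment administration section of CRF Chemotherapy Report".

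The capecitabine schedule is the same in both documents: Protocol 7.1.1.2 has "14 days starting on Day 1" and SAP 7.4.1 has "1000 mg/m² capecitabine orally twice daily for 14 days from day 1", in 21-day cycles, four in all.

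**The concern.** Adding one full cycle length to the last dosing date gives the end of the last cycle only when that date is day 1 of the cycle. This holds for oxaliplatin. It does not hold for capecitabine, whose last day is day 14, so the added 21 days run 13 days beyond the cycle. The planned weekly dose assumes exactly 21 days per cycle, so the two sides of the ratio use different lengths.

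The capecitabine columns of Tables 20 and 21 would then understate what was delivered. A patient with no reduction and no delay would show 100% for oxaliplatin beside 86.6% for capecitabine, which a reader would take as a real shortfall. The bias also changes with the number of cycles and the stopping day, so a reader could not correct it with a single factor. The SAP lists dosing data among its safety endpoints (SAP 4.3), so these tables should mean what they appear to mean.

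**Working it through.** **Inputs**
- Capecitabine 1000 mg/m² twice daily for 14 days (Protocol 7.1.1.2; SAP 7.4.1): 1000 × 2 × 14 = 28,000 mg/m² per cycle.
- Cycle length 21 days, four cycles (SAP 7.4.1): 4 × 21 = 84 days = 12 weeks.
- Day count: last date minus first date, plus 21, divided by 7 (SAP 7.4.1).
- Table 21 cut-points: 60, 80 and 90% (SAP 7.4.3).

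**The plan's own reference**
28,000 / 3 weeks = 9333.3 mg/m²/week. This matches SAP 7.4.3 and confirms that the reference uses exact 21-day cycles.

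**Rule as written, four full-dose, on-time cycles**
- Cycles start on days 1, 22, 43 and 64. The last capecitabine day is 64 + 13 = 77.
- Duration: 77 − 1 + 21 = 97 days = 13.857 weeks, which is 13 days more than 84.
- Cumulative dose: 4 × 28,000 = 112,000 mg/m².
- Dose intensity: 112,000 / 13.857 = 8082 mg/m²/week.
- Relative dose intensity: 8082 / 9333.3 = 84/97 = 86.6%.

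**Same patient, last date taken as day 1 of the last cycle**
64 − 1 + 21 = 84 days = 12 weeks; 112,000 / 12 = 9333.3; 100%.

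**Other numbers of full-dose, on-time cycles**

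| Cycles | True days | Days by the rule | Reported |
|---|---|---|---|
| 4 | 84 | 97 | 86.6% |
| 3 | 63 | 76 | 82.9% |
| 2 | 42 | 55 | 76.4% |
| 1 | 21 | 34 | 61.8% |

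**Effect on the Table 21 categories (four on-time cycles)**
- Dividing the cut-points by 84/97 shows the true values at which they act: 60% at 69.3%, 80% at 92.4%, 90% at 103.9%. A true 90% is reported as 0.90 × 84/97 = 77.9%.
- Example: two cycles at 1000 and two at 750 mg/m² twice daily deliver 2 × 28,000 + 2 × 21,000 = 98,000 mg/m². Over 12 weeks this is 8166.7 mg/m²/week, or 87.5%. Over 13.857 weeks it is 7072 mg/m²/week, or 75.8%, one category lower.
- These shifted cut-points apply to dose reductions without delay. With one 7-day delay at full dose, the true value is 84/91 = 92.3% and the reported value is 84/104 = 80.8%.
- The gap shrinks when capecitabine stops early. If it stops on day 7 of cycle 4, the dose is 98,000 mg/m² (true 87.5%), the duration is 70 − 1 + 21 = 90 days, and the reported value is 87.5% × 84/90 = 81.7%.

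**Other drugs under the same rule**
- CAPOX oxaliplatin: 63 + 21 = 84 days, 100%. FOLFOX day-1 drugs: 100%.
- Infusional 5-FU over six cycles: 84/85 = 98.8% if the last day is day 2, or 84/86 = 97.7% if it is day 3. No category changes at planned dose.

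**Sensitivity to the day count**
An inclusive count (one day more), or an evening start that moves the last dose to day 15, gives 98 days and 84/98 = 85.7%.

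**Table 17**
If the last capecitabine date is used in SAP 7.4.1, duration is 13.9 weeks instead of 12.0.

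**The case against.** The strongest reply is that the dates come from the Chemotherapy Report, which is not in the documents, and that the form may well work by cycle. Adding exactly one cycle length makes sense only if the last date is day 1 of a cycle. Protocol Appendix III has the form completed after each cycle. SAP 7.2.1 shows that it carries a cycle-level date, "day 1 of reporting period on CRF Chemotherapy Report", and uses no later date from that form when finding when a patient was last known alive. Elsewhere the trial counts from the start of the last cycle, as in SAP 7.5: "after first dose of last cycle of chemotherapy". On that reading the programmed result is 100% and only the wording is loose.

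It may also be said that these tables are descriptive and carry no decision rule. Tables 16, 18 and 19 (cycles, modifications, cumulative dose) would still show full delivery. The number of CAPOX patients among the 58 is not given, so the effect on the study's summary cannot be estimated.

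The points on scope stand. The point on intent is plausible but remains inference: no section says that the last day of administration means day 1 of the last cycle. Where the SAP wants such a date it names it, as the two phrases just quoted show. Day-level capecitabine information is also collected: Protocol Appendix III provides for a daily diary, with data entered by the site as required. Two careful programmers could therefore report 86.6% and 100% for the same patient.

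**Conclusion.** The rule is wrong as written for capecitabine. Followed literally, it adds 13 days to the duration and turns 100% into 86.6% for four full-dose, on-time cycles, with lower values for fewer cycles (82.9, 76.4 and 61.8% for three, two and one). At planned dose and schedule the category of 90% or more is out of reach.

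This rests on one assumption: that the last day of administration is the last day capecitabine was taken, which is what the text says. If the date actually used is day 1 of the last cycle, the error does not occur.

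The effect is confined to the capecitabine column of Tables 20 and 21, about 1 to 2% for infusional 5-FU, and Table 17 only if the last capecitabine date is used there. Oxaliplatin, cycle counts, cumulative dose, efficacy and adverse-event analyses are untouched. It should be corrected, but it does not bear on the trial's main conclusion.

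**What to change.** In SAP 7.4.1 and 7.4.3, define duration in weeks as (day 1 of the last cycle − day 1 of the first cycle + 14 for FOLFOX or 21 for CAPOX) / 7, and state that the CRF date used is day 1 of each cycle. In 7.4.3 keep the existing restriction to cycles in which the drug in question was prescribed, so that a drug stopped early is still measured over its own cycles.

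This restores 84 days, 9333.3 mg/m²/week and 100% for the fully compliant patient, and also removes the small infusional 5-FU discrepancy. The cost is one sentence in each of the two sections. No new data are needed if the form records day 1 of each cycle, and no dose or treatment rule changes. If day 1 was intended throughout, the sentence simply puts it on record.
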